### 3. OBJECTIVES AND ENDPOINTS

Objectives	Endpoints
Primary – Phase 2	

 
To select maximally tolerated dose for use in Phase 3, and to assess the effect of dociparstat on disease progression in participants with severe COVID-19
 
	
 
Incidence of AEs, severe AEs, and SAEs
 
Proportion of participants who are alive and free of invasive mechanical ventilation through Day 28
 

Primary – Phase 3	

 
To assess the effect of dociparstat on disease progression in participants with severe COVID-19
 
	
 
Proportion of participants who are alive and free of invasive mechanical ventilation through Day 28
 

Key Secondary	

 
To assess the effect of dociparstat on mortality
 
	
 
All-cause mortality through Day 28
 

Secondary	

 
To determine additional evidence of a therapeutic effect of dociparstat in participants with severe COVID-19
 
	
 
Time to invasive mechanical ventilation or all-cause mortality
 
Time to all-cause mortality
 
Proportion of participants who are alive, discharged from the hospital, and not using home oxygen at fixed time points (Days 8, 14, and 28)
 
Clinical status assessed by the NIAID ordinal scale at fixed time points (Days 8, 14, and 28)
 
Time to clinical improvement, defined as time to at least a 2-grade improvement from baseline on the NIAID ordinal scale
 
Number of ventilator-free days from baseline through Day 28
 
Time to hospital discharge
 
Time to resolution of fever, defined as temperature <math>\leq 99.0^{\circ}\text{F}</math> (<math>\leq 37.2^{\circ}\text{C}</math>) and no antipyretic use within the preceding 48 hours (participants with baseline fever only)
 
Change from baseline in C-reactive protein level
 
Change from baseline in serum ferritin level
 
Change from baseline in lactate dehydrogenase level
 
Change from baseline in d-dimer level
 
Daily average of prednisone-equivalent corticosteroid dose through Day 28
 

Objectives	Endpoints

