#### **4.4. End of Study Definition**

A participant is considered to have completed the study if he/she has completed the Day 28 follow-up visit.

The end of the study is defined as the date of the last visit of the last participant in the study.

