#### **7.4. Lost to Follow-up**

A participant will be considered lost to follow-up if he/she repeatedly fails to return for scheduled visits and the study center is unable to contact the participant.

The following actions must be taken if a participant fails to return to the clinic for a required study visit:

- The site must attempt to contact the participant and reschedule the missed visit as soon as possible and counsel the participant on the importance of maintaining the assigned visit schedule and ascertain whether or not the participant wishes to and/or should continue in the study.
- Before a participant is deemed lost to follow-up, the investigator or designee must make every effort to regain contact with the participant (where possible, 3 telephone calls and, if necessary, a certified letter to the participant's last known mailing address or local equivalent methods). These contact attempts should be documented in the participant's medical record.

- Should the participant continue to be unreachable, he/she will be considered to have withdrawn from the study. The sponsor may retain and continue to use any data collected.
- The site should also make every effort to verify the participant's vital status with the participant's regular/non-study physician(s).

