3. DERIVATIONS AND DEFINITIONS

Kaplan-Meier estimates

Time to xxx (days): Days are calculated as (start date/time – first study drug date/time)/24h). Time will be censored at last individual date/time reported.

Worst-case results in 2 scenarios for missing time-values:

1. Missing time for negative events will be imputed with “00:01”, missing time for censored observations will be imputed with “23:59”.

Negative events are:

- Time to first invasive mechanical ventilation or ECMO
- Time to first invasive mechanical ventilation, ECMO or all-cause mortality
- Time to all-cause mortality

2. Missing time for positive events will be imputed with “23:59”, missing time for censored observations will be imputed with “00:01”.

Positive events are:

- Time to clinical improvement
- Time to hospital discharge

In addition, to avoid bias in the positive events, deaths occurring prior to the positive event being observed will be censored at Day 28.

Ventilator-free days

Ventilator-free days are only counted from baseline through Day 28 or end of study, whichever comes first. They are derived based on the eCRF data collected on the Ventilator/Oxygen/Medical Care Status CRF page, Ventilator-free days are all days where Ventilator/Oxygen/Medical Care Status is not equal “Invasive Mechanical Ventilation or extracorporeal membrane oxygenation (ECMO)”.

Ventilator days are defined as cumulative rounded number of days with Ventilator/Oxygen/Medical Care Status = “Invasive Mechanical Ventilation or extracorporeal membrane oxygenation (ECMO)” divided by 24 h. Missing time for start will be imputed with “00:01”, missing time for stop will be imputed with “23:59”.

Study duration in days is defined as: Date of study completion (or date of early study discontinuation) – date of first study treatment + 1. For subjects randomized but not treated the date of randomization will be used instead of first study treatment date. The maximum study duration is set to 28 days, even if study completion or study discontinuation is after 28 days.

Ventilator-free days are defined as: study duration - number of ventilator days. For subjects who died during the course of the study, the number of ventilator-free days will be defined as 0.

Randomized, but not treated subjects:

The following rules will apply for randomized subjects without receiving study treatment, if not stated otherwise:

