4	xx (xx.x)	xx (xx.x)	xx (xx.x)	xx (xx.x)
5	xx (xx.x)	xx (xx.x)	xx (xx.x)	xx (xx.x)
6	xx (xx.x)	xx (xx.x)	xx (xx.x)	xx (xx.x)
7	xx (xx.x)	xx (xx.x)	xx (xx.x)	xx (xx.x)
8	xx (xx.x)	xx (xx.x)	xx (xx.x)	xx (xx.x)
...				
28	xx (xx.x)	xx (xx.x)	xx (xx.x)	xx (xx.x)
n	xxx	xxx	xxx	xxx
Mean	xx.x	xx.x	xx.x	xx.x
SD	xx.x	xx.x	xx.x	xx.x
Median	xx	xx	xx	xx
Q1, Q3	xx, xx	xx, xx	xx, xx	xx, xx
Min, Max	xx, xx	xx, xx	xx, xx	xx, xx

N = Number of subjects in a specific group; n = Number of subjects with data available; Percentages are based on N; SD: Standard deviation; Q1, Q3: First, third quartile; Min: minimum; Max: maximum.

Ventilator-free days are only counted through the date of early study discontinuation, study completion date or Day 28, whichever comes first. For subjects who die during the course of the study, number of ventilator-free days is defined as 0.

Page X of Y

(Notes for programmer:

Include only the categories of Days (0-28) in the table which are available in the data
)

Table 24: Time to last hospital discharge - ITT Set

	DSTAT 0.25 N=xxx	Cohort 1 PBO N=xxx	DSTAT 0.325 N=xxx	Cohort 2 PBO N=xxx
Number of subjects discharged from hospital, n (%) (a)	xx (xx.x)	xx (xx.x)	xx (xx.x)	xx (xx.x)
Kaplan-Meier estimates (b)				
Number of censored subjects, n (%) (b)	xx (xx.x)	xx (xx.x)	xx (xx.x)	xx (xx.x)
Number of subjects alive and still in hospital	xx (xx.x)	xx (xx.x)	xx (xx.x)	xx (xx.x)
Death	xx (xx.x)	xx (xx.x)	xx (xx.x)	xx (xx.x)
Time to hospital discharge (days) (b)				
25% Quartile (95% CI)	x.x (x.xx, x.xx)	x.x (x.xx, x.xx)	x.x (x.xx, x.xx)	x.x (x.xx, x.xx)
Median (95% CI)	x.x (x.xx, x.xx)	x.x (x.xx, x.xx)	x.x (x.xx, x.xx)	x.x (x.xx, x.xx)
75% Quartile (95% CI)	x.x (x.xx, x.xx)	x.x (x.xx, x.xx)	x.x (x.xx, x.xx)	x.x (x.xx, x.xx)

N = Number of subjects in a specific group; n = Number of subjects with data available; Percentages are based on N;
 (a) Subjects discharged from hospital will be counted as event.

(b) Kaplan-Meier estimates: Subjects discharged from hospital will be counted as event. Subjects who are still in the hospital or died in the hospital will be censored.

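### The rule that sets ventilator-free days to 0 for death has no Day 28 limit, although the endpoint stops at Day 28

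*SAP*

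**What the plan says.** Protocol Section 3 lists the secondary endpoint as "Number of ventilator-free days from baseline through Day 28".

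SAP Section 3 gives the formula: "Ventilator-free days are defined as: study duration - number of ventilator days". It caps the first term: "The maximum study duration is set to 28 days, even if study completion or study discontinuation is after 28 days". The death rule follows, without a cap: "For subjects who died during the course of the study, the number of ventilator-free days will be defined as 0". The Table 23 footnote repeats the rule in nearly the same words: "For subjects who die during the course of the study, number of ventilator-free days is defined as 0". It does so after saying where counting stops: "Ventilator-free days are only counted through the date of early study discontinuation, study completion date or Day 28, whichever comes first".

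Three protocol provisions decide what that rule covers:

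- **End of follow-up.** Section 4.4 says: "A participant is considered to have completed the study if he/she has completed the Day 28 follow-up visit". The Schedule of Activities allows that visit 3 days either side of Day 28, so it can fall on Days 25 to 31.
- **Deaths after withdrawal.** Section 7.4 treats an unreachable participant as withdrawn, but adds: "The site should also make every effort to verify the participant's vital status".
- **Late deaths.** Section 8.4.5 makes a death reportable if the causal event began by Day 28, whatever the date of death.

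**The concern.** The endpoint has a fixed horizon, but the death rule depends on whether the participant was in the study. Those two periods end on different days for different people. The SAP allows for this in the duration count, through the 28-day cap, but not in the death rule.

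This leaves two gaps. A death just after Day 28 can wipe out days that were validly accrued inside the window. A death inside the window, learned of after the participant has left or finished the study, has no stated handling. In either case the score could depend on when the last visit was booked, or on how a programmer reads an undefined phrase. With arms of 4 to 8 participants, one such person visibly changes the mean.

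**Working it through.** No sample size, power or alpha figure depends on this rule, so there is no plan figure to reproduce. The check applies the SAP formula to test cases under three readings of the death rule.

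**Formula.** Ventilator-free days = min(study duration, 28) − ventilator days, or 0 if the death rule applies.

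**Readings.**
- A: death while the participant is still in the study.
- B: death on or before Day 28.
- C: any recorded death.

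| Case | A | B | C |
|---|---|---|---|
| Death Day 29 or 31, final visit not yet done, never ventilated | 0 | 28 − 0 = 28 | 0 |
| Death Day 30, final visit not yet done, 9 ventilator days | 0 | 28 − 9 = 19 | 0 |
| Death Day 31, final visit not yet done, 14 ventilator days | 0 | 28 − 14 = 14 | 0 |
| Final visit Day 28, death Day 29, never ventilated | 28 | 28 | 0 |
| Final visit Day 25, death Day 27, never ventilated | 25 | 0 | 0 |
| Withdrew Day 10, known death Day 20, never ventilated | 10 | 0 | 0 |
| Withdrew Day 10, known death Day 20, 4 ventilator days | 10 − 4 = 6 | 0 | 0 |
| Withdrew Day 27, known death Day 28, never ventilated | 27 | 0 | 0 |

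Only reading B respects the Day 28 horizon in every row. Reading A fails in both directions. Reading C fails only for deaths after Day 28.

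**Comparison with Table 18.** Its first row counts participants alive and free of invasive ventilation or ECMO through Day 28. A never-ventilated participant who dies on Day 29 can meet that description and still score 0 in Table 23. A participant who had been ventilated would not be in that row, so this conflict is limited to the never-ventilated.

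**Effect on an arm mean** (change in score divided by n). Arms are 6 and 6 in Cohort 1. Cohort 2 is 8 and 4 in Protocol Section 4.1, but 6 and 6 in the SAP Introduction.

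| Change for one participant | n=4 | n=6 | n=8 |
|---|---|---|---|
| 28 versus 0 | 28/4 = 7.0 | 28/6 = 4.7 | 28/8 = 3.5 |
| 10 versus 0 | 10/4 = 2.5 | 10/6 = 1.7 | 10/8 = 1.25 |

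**Frequency, on assumption only.** The documents give no late mortality rate. Suppose 0.2-0.5% die per day after Day 28 and half of the final visits are held about 2 days late. Then 0.5 × 2 × 0.2% = 0.2% to 0.5 × 2 × 0.5% = 0.5% of participants die after Day 28 but before their visit. Among the 24 in Cohorts 1 and 2 that is 24 × 0.002 = 0.05 to 24 × 0.005 = 0.12 people. It includes ventilated participants, who lose fewer than 28 days.

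**The case against.** The best defence is that the SAP's phrase already means Day 28. The Schedule of Activities footnote on adverse events equates completing the study with Day 28, protocol Appendix 2 describes death during participation as running from randomization through Day 28, and the title of Table 23 ends there too. On that reading neither gap exists. Alternatively, Protocol Section 4.4 ends the study at the last participant's last visit. On that trial-level reading a death after withdrawal would normally score 0, and only the late-death problem remains.

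Both readings are tenable, but the SAP states neither. Protocol Section 8.4.5 describes death during participation as running through follow-up. The SAP itself expects completion after Day 28 in some participants. Where its authors wanted a Day 28 limit on deaths they wrote one, as in the Table 22 footnote on participants who die without improvement.

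A reader might also infer that ventilator-free days contradict the mortality count in Table 19. The documents do not support that: the Table 19 death count has no Day 28 cutoff either, nor does the event count in Table 18, so a Day 29-31 death would count there as well. The only demonstrable mismatch is with the first row of Table 18.

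The practical stakes are also fairly described as small. Protocol Section 9.4 makes the Cohort 1 and 2 analyses descriptive and gives Phase 3 its own SAP. Table 23 shows the full distribution, median and quartiles beside the mean. Table 2 lists death dates for treated participants, which would expose a case. Withdrawal from follow-up is not the default after stopping treatment (Protocol Section 7.3).

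**Conclusion.** The point holds as a gap in a derivation rule. The death window for ventilator-free days is not stated, and the literal wording is out of line with the endpoint's own horizon.

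Two stronger conclusions are tempting and go too far. One is that the rule certainly produces errors in both directions. That requires reading the phrase as each participant's own time in the study, and on known deaths after withdrawal or early completion the SAP is silent rather than wrong. The other is that every late death costs 28 days. That is the maximum, reached only by someone never ventilated.

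The arm-mean shifts are therefore upper limits for a single case, and the expected number of late-death cases is well below one under the mortality and visit-timing assumptions shown. Alpha, power and the primary endpoint are untouched. This is a minor correction, worth making because it removes discretion from a score that one participant can dominate.

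**What to change.** In SAP Section 3 and in the Table 23 footnote, replace the death sentence with:

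*For subjects known to have died on or before Day 28, whether or not they had discontinued or completed the study, ventilator-free days = 0; deaths after Day 28 do not change the count.*

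Day 28 should be counted from first study treatment, or from randomization for untreated participants, as the SAP already does for study duration.

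The cost is one sentence in two places and one date condition in the program. No new data are needed, since the protocol already asks for the date of death and for vital status after loss to follow-up.
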